5.0 Subject Disposition

The total number of subjects who were screened, enrolled (randomized), and treated will be summarized. Reasons for exclusion, including screen failure, will be summarized. A summary of subject accountability will be provided where the number of subjects in each of the following categories will be summarized for each treatment group:

- Subjects enrolled (randomized) in the study;
- Subjects who took the dose of study drug;
- Subjects who prematurely discontinued study drug (all reasons and primary reason).

For end of study participation, the number and percentage of subjects who completed the protocol defined follow-up period (or did not with associated reasons) will be summarized overall and by treatment group.

6.0 Study Drug Duration and Compliance

Not applicable.

7.0 Demographics, Baseline Characteristics, Medical History, and Prior/Concomitant Medications

Demographics, baseline or disease characteristics, medical history, and prior and concomitant medications will be summarized for the SAS overall and by treatment group. Categorical variables will be summarized with the number and percentage of subjects; percentages will be calculated based on the number of non-missing observations. Continuous variables will be summarized with descriptive statistics (number of non-missing observations, mean and standard deviation, median, minimum and maximum).

7.1 Demographics and Baseline Characteristics

Continuous demographic variables include age. Categorical demographic variables include sex, ethnicity and race.

7.2 Medical History

Medical history data will be coded using the Medical Dictionary for Regulatory Activities (MedDRA). The actual version of the MedDRA coding dictionary will be noted in the statistical tables and clinical study report. The number and percentage of subjects in each medical history category (by MedDRA system organ class and preferred term) will be summarized overall and by treatment group. The system organ class (SOC) will be presented in alphabetical order, and the preferred terms will be presented in alphabetical order within each SOC. Subjects reporting more than one condition/diagnosis will be counted only once in each row (SOC or preferred term).

7.3 Ophthalmic Medical History

Ophthalmic medical history is defined as indicated on the medical history eCRF form marked 'OD', 'OS' or 'OU' to the question of the location of the medical history.

Ophthalmic medical history data will be coded using the Medical Dictionary for Regulatory Activities (MedDRA). The actual version of the MedDRA coding dictionary will be noted in the statistical tables and clinical study report. The number and percentage of subjects in each ophthalmic medical history category (by MedDRA system organ class and preferred term) will be summarized overall and by treatment group. The system organ class (SOC) will be presented in alphabetical order, and the preferred terms will be presented in alphabetical order within each SOC. Subjects reporting more than one condition/diagnosis will be counted only once in each row (SOC or preferred term).

7.4 Prior and Concomitant Medications

Prior and concomitant medications will be summarized by generic name. A prior medication is defined as any medication taken prior to the date of the study drug.

A concomitant medication is defined as any medication that started prior to the date of the first dose of study drug and continued to be taken after the first dose of study drug or any medication that started on or after the date of the first dose of study drug. The number and percentage of subjects taking medications will be summarized by generic drug name based on the World Health Organization (WHO) Drug Dictionary for both prior and concomitant medications.

8.0 Handling of Potential Intercurrent Events for the Primary and Key Secondary Endpoints

Not applicable.

9.0 Efficacy Analyses

Not applicable.

10.0 Safety Analyses

10.1 General Considerations

Safety data will be summarized for the SAS. Safety summaries will be presented by treatment group. For the safety analysis, subjects are assigned to a treatment group based on the treatment actually received, regardless of the treatment randomized.

Study eye is defined as the eye that received DEX PS DDS Implant.

10.2 Adverse Events

Adverse events (AEs) will be summarized and presented using primary MedDRA System Organ Classes (SOCs) and preferred terms (PTs) according to the version of the MedDRA coding dictionary used for the study at the time of database lock. The actual version of the MedDRA coding dictionary used will be noted in the AE tables and in the clinical study report. Specific adverse events will be counted once for each subject for calculating percentages, unless stated otherwise. In addition, if the same adverse event occurs

multiple times within a subject, the highest severity and level of relationship to investigational product will be reported.

10.2.1 Treatment-Emergent Adverse Events

Treatment-emergent AEs are defined as any AE with the onset that is after the first dose of study drug. Events where the onset date is the same as the study drug start date are assumed to be treatment-emergent. Each treatment-emergent AE will be determined as ocular or non-ocular AE. The ocular treatment-emergent AE is defined as indicated on the AE form of eCRF marked “OD” or “OS” to the question of “what was the location of the adverse event All treatment-emergent AEs, ocular treatment-emergent AEs in either the study eye or fellow eye, and non-ocular AEs will be summarized overall, as well as by primary MedDRA SOC and Preferred Term. The SOCs will be presented in alphabetical order, and the PTs will be presented in alphabetical order within each SOC.

The number and percentage of subjects experiencing treatment-emergent AEs will be summarized.

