10.2.2 Adverse Event Overview

An overview of AEs will be presented consisting of the number and percentage of subjects experiencing at least one event for each of the following AE categories:

- Any treatment-emergent AE
- Any treatment-emergent AE related to study drug according to the investigator
- Any severe treatment-emergent AE
- Any serious treatment-emergent AE
- Any treatment-emergent AE leading to death
- Any ocular treatment-emergent AE
- Any AEs of Special Interest
- All deaths

- TEAEs related to COVID-19 infection.

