10.2.6 Adverse Events of Special Interest

There are no protocol-specific AEs of special interest.

However, AEs possibly related to DEX PS DDS implant position and administration will be tabulated by PT. These AEs include, but not limit to, conjunctival hemorrhage, conjunctival tear cataract, lens or lenticular abnormality or change from baseline, vitreous

haze, vitreous hemorrhage, vitreous leak, retinal hemorrhage, retinal tear, retinal hole, retinal detachment, other retinal abnormality or change, intraocular inflammation, blindness, visual acuity or vision decrease. Also, abnormality or change of best corrected visual acuity (BCVA) (≥ 2 lines or more worse than baseline) and IOP change by 10 mmHg from baseline will be reported as AE, and will be included.

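### The SAP's rule for an ocular TEAE lists OD and OS but not OU, so an adverse event recorded as bilateral, if the AE form allows that, would be tabulated as non-ocular

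*SAP*

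**What the plan says.** SAP 10.2.1 sets up a two-way split with no third class: "Each treatment-emergent AE will be determined as ocular or non-ocular AE". The test for the ocular class is the answer to the location question on the AE form: "The ocular treatment-emergent AE is defined as indicated on the AE form of eCRF marked “OD” or “OS". OU is not listed, and no separate definition of non-ocular is given.

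The split feeds several outputs. SAP 10.2.1 says that "ocular treatment-emergent AEs in either the study eye or fellow eye, and non-ocular AEs will be summarized overall" and by system organ class and preferred term. SAP 10.2.3 repeats the same groups by relationship, severity and subject. SAP 10.2.2 has the overview row "Any ocular treatment-emergent AE". SAP 10.1 fixes which eye is which: "Study eye is defined as the eye that received DEX PS DDS Implant".

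For history, SAP 7.3 takes the same location-based approach with a longer list: "Ophthalmic medical history is defined as indicated on the medical history eCRF form marked 'OD', 'OS' or 'OU". Protocol Appendix D gives OU as the abbreviation for both eyes.

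One relevant table does not use the location code. Under SAP 10.2.6, "AEs possibly related to DEX PS DDS implant position and administration will be tabulated by PT".

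**The concern.** Two sections of one SAP identify eye-related records by location code, and only one of them accepts the bilateral code. A programmer following both literally would treat OU as an eye location in the history tables and as not an eye location in the AE tables.

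A second gap lies behind the first. A programmer who does treat OU as ocular still has no rule for whether the event goes in the study-eye table, the fellow-eye table or both. SAP 10.2 and 10.2.3 count a specific event once per subject, so placing it in both tables needs to be stated.

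Bilateral findings are possible in this design. Acuity, pressure, slit lamp and ophthalmoscopy are done in both eyes at screening, Day 2 and Day 7 (Protocol Appendix D). Treatment of the non-study eye is unrestricted (Protocol 5.4, Table 1). At stake are the ocular AE rates by arm and by eye, which bear on a study where only the applicator changes (Protocol 2.2). Outputs could also disagree with each other. A pressure or acuity change reported as an AE and coded OU would appear in the SAP 10.2.6 table of administration-related events, yet be filed as non-ocular elsewhere.

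**Working it through.** **Step 1. Apply the two location rules to each code.**

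| Location code | Rule in SAP 10.2.1 (OD, OS) | Rule in SAP 7.3 (OD, OS, OU) |
|---|---|---|
| OD | ocular | ocular |
| OS | ocular | ocular |
| OU | non-ocular | ocular |
| no eye location | non-ocular | non-ocular |

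The rules differ only for OU. It fails the ocular test in SAP 10.2.1, and the two-way split leaves non-ocular as the only remaining class.

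**Step 2. Reproduce the planned arm sizes.** Protocol 7.8 and SAP 2.4 give minimums of 30 and 15 eyes, dropout of about 15% and a total of about 54. The formula is n / (1 − dropout), rounded up.

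- Updated applicator: 30 / 0.85 = 35.3, so 36.
- Currently approved applicator: 15 / 0.85 = 17.6, so 18.
- Total: 36 + 18 = 54, which matches the plan and the 2:1 ratio.

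**Step 3. Effect of one affected subject.** An affected subject is one whose only ocular TEAE is coded OU. A subject who also has an OD or OS event still counts in the overview row, so that rate does not move. For k affected subjects in an arm of n, the ocular rate falls by 100 × k / n percentage points. The documents do not give k. The range 0 to 3 is an assumption for illustration only.

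| k (assumed) | n = 36 | n = 18 | n = 30 (minimum) | n = 15 (minimum) |
|---|---|---|---|---|
| 0 | 0 | 0 | 0 | 0 |
| 1 | 2.8 | 5.6 | 3.3 | 6.7 |
| 2 | 5.6 | 11.1 | 6.7 | 13.3 |
| 3 | 8.3 | 16.7 | 10.0 | 20.0 |

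The non-ocular rate rises by the same amount if the affected subject has no other non-ocular event.

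**Step 4. Where the event would still appear.** It stays in the all-TEAE summaries, including those by severity and relationship (SAP 10.2.1 to 10.2.3). If serious, it is in the SAP 10.2.5 table. If its term is listed, it is in the preferred-term table of SAP 10.2.6 and Appendix B. Acuity, pressure, slit-lamp and ophthalmoscopy findings are summarised from the examination data for both eyes (SAP 10.5.1 to 10.5.4), whatever the AE coding.

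**The case against.** The strongest objection is that the AE form cannot be seen. The two lists may simply mirror two forms with different options: history can carry one bilateral diagnosis, while AEs may be entered eye by eye so that study-eye and fellow-eye tables can be built. In that case OD or OS covers every ocular entry and nothing is misfiled. This stands. The history form's OU option makes one on the AE form plausible but does not prove it.

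A sensible programmer might also read ocular events in either eye as including events in both, since SAP 10.2.1 never defines non-ocular. That reading is reasonable, but it depends on someone departing from the stated test, and it still leaves the choice of eye table open.

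The importance is limited too. Protocol 3.5 and SAP 3.2 say the study is not designed to assess safety, and there is no hypothesis (Protocol 3.1, SAP 2.1). Only one eye is treated, so an applicator-related event should mostly be unilateral. That also stands.

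A reader might infer that bilateral events will be lost, or that the study's main safety result is biased. The documents support neither. Any misfiling is conditional on the form, the event stays in the other tables listed in Step 4, and the outputs are descriptive.

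**Conclusion.** The point holds conditionally and is minor. SAP 10.2.1 and 7.3 use different location lists, and nothing else in the SAP or protocol sends a bilateral AE to the ocular tables or says it is entered as two records. If the AE form allows OU, the stated rule misfiles such an event.

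The cost is 2.8 points per affected subject in the updated-applicator arm and 5.6 in the comparator, assuming that all 36 and 18 planned subjects are treated and that the subject has no other ocular TEAE. The number affected cannot be derived from the documents and may be zero. Sample size and inference are untouched, because no test is planned.

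**What to change.** First confirm how the AE form records a bilateral event. Then make one of two changes to SAP 10.2.1:

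- **If OU is an allowed answer:** define an ocular TEAE as one with location OD, OS or OU. State that an OU event is counted in both the study-eye and the fellow-eye tables, and that the subject is counted once in "Any ocular treatment-emergent AE".
- **If the form records each eye separately:** state that bilateral events are entered as separate OD and OS records.

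The cost is one or two SAP sentences and, for the first option, one programming condition plus the rule for both eye tables. The first option has a small downside: a single OU record applies one severity rating and one relationship rating to the treated and the untreated eye alike. Separate records avoid that.

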10.2.2 Adverse Event Overview

An overview of AEs will be presented consisting of the number and percentage of subjects experiencing at least one event for each of the following AE categories:

- Any treatment-emergent AE
- Any treatment-emergent AE related to study drug according to the investigator
- Any severe treatment-emergent AE
- Any serious treatment-emergent AE
- Any treatment-emergent AE leading to death
- Any ocular treatment-emergent AE
- Any AEs of Special Interest
- All deaths

- TEAEs related to COVID-19 infection.

10.2.3 Treatment-Emergent Adverse Events by SOC and/or PT

Treatment-emergent AEs, ocular treatment-emergent AEs in either the study eye or fellow eye, and non-ocular AEs will be summarized by SOC and PT; by maximum relationship to study procedure as assessed by the investigator (e.g., reasonable possibility or no reasonable possibility) and SOC and PT; by maximum severity and SOC and PT; and by subject number and SOC and PT. Specific adverse events will be counted once for each subject for calculating percentages, unless stated otherwise. In addition, if the same adverse event occurs multiple times within a subject, the highest severity and level of relationship to investigational product will be reported.

10.2.4 Treatment-Emergent Adverse Events per Patient-Years of Exposure

Not applicable.

10.2.5 SAEs (Including Deaths) and Adverse Events Leading to Study Discontinuation

SAEs (including deaths) and AEs leading to study discontinuation will be summarized by SOC and PT and in listing format.

10.2.6 Adverse Events of Special Interest

There are no protocol-specific AEs of special interest.

However, AEs possibly related to DEX PS DDS implant position and administration will be tabulated by PT. These AEs include, but not limit to, conjunctival hemorrhage, conjunctival tear cataract, lens or lenticular abnormality or change from baseline, vitreous

haze, vitreous hemorrhage, vitreous leak, retinal hemorrhage, retinal tear, retinal hole, retinal detachment, other retinal abnormality or change, intraocular inflammation, blindness, visual acuity or vision decrease. Also, abnormality or change of best corrected visual acuity (BCVA) (≥ 2 lines or more worse than baseline) and IOP change by 10 mmHg from baseline will be reported as AE, and will be included.

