5.4 Prior and Concomitant Therapy

Allowed concomitant medications/therapies are presented in [Table 1](#).

Table 1. Allowed Concomitant Medications/Therapy

Allowed Concomitant Medications/Therapy	Comments/Notes
IOP-lowering treatment	If elevated IOP is observed in the SE after DEX PS DDS Implant administration during the study, IOP lowering treatment will be initiated at the discretion of the investigator.
Medications required for treatment administration	Medications required for DEX PS DDS Implant administration are permitted at the investigator's discretion.
Use of systemic NSAIDs	Systemic NSAIDs regularly used prior to enrollment will be allowed to continue during the study and should be administered at a dosage that remains constant throughout the course of the study.
Treatment in the non-SE	Treatment in the non-SE is not restricted during the study, and the non-SE will receive standard of care per investigator discretion.

DEX PS DDS = Dexamethasone Posterior Segment Drug Delivery System; IOP = intraocular pressure; NSAIDs = nonsteroidal anti-inflammatory drug; SE = study eye

Any medication or vaccine (including over-the-counter or prescription medicines, vitamins, and/or herbal supplements) that the subject is receiving at the time of enrollment or receives during the study must be recorded from Screening/Baseline Visit prior to study drug administration through the Day 7/Premature Discontinuation (PD) Visit.

Any questions regarding concomitant or prior therapy should be raised to the AbbVie emergency contact. Information regarding potential drug interactions with DEX PS DDS Implant can be located in the DEX PS DDS investigator's brochure.

Subjects must be able to safely discontinue any prohibited medications as described in the eligibility criteria. Subjects must be consented for the study prior to discontinuing any prohibited medications for the purpose of meeting study eligibility.

COVID-19 Pandemic-Related Vaccination Guidance

Given the ongoing COVID-19 pandemic, selected non-live vaccines (e.g., messenger ribonucleic acid, non-replicating viral vector, protein subunit, etc.) to prevent severe acute respiratory syndrome coronavirus 2 (SARS-CoV-2) infection may be administered during screening or the study period, as long as components of the vaccine are not contraindicated.

The decision to receive a locally available vaccine should be based on local guidance and an individual discussion between the treating physician and the subject.

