Persistent or Significant Disability/Incapacity	An event that results in a condition that substantially interferes with the activities of daily living of a study subject. Disability is not intended to include experiences of relatively minor medical significance such as headache, nausea, vomiting, diarrhea, influenza, and accidental trauma (e.g., sprained ankle).
Important Medical Event Requiring Medical or Surgical Intervention to Prevent Serious Outcome	An important medical event that may not be immediately life-threatening or result in death or hospitalization, but based on medical judgment may jeopardize the subject and may require medical or surgical intervention to prevent any of the outcomes listed above (i.e., death of subject, life threatening, hospitalization, prolongation of hospitalization, congenital anomaly, or persistent or significant disability/incapacity). Additionally, any elective or spontaneous abortion or stillbirth is considered an important medical event. Examples of such events include allergic bronchospasm requiring intensive treatment in an emergency room or at home, blood dyscrasias or convulsions that do not result in inpatient hospitalization, or the development of drug dependency or drug abuse.

All AEs reported from the time of study drug administration through study exit will be collected, whether solicited or spontaneously reported by the subject. In addition, study procedure-related serious and nonserious AEs will be collected from the time the subject signs the study-specific informed consent.

AbbVie will be responsible for Suspected Unexpected Serious Adverse Reactions reporting for DEX PS DDS in accordance with global and local requirements.

Adverse events will be monitored throughout the study to identify any of special interest that may indicate a trend or risk to subjects.

Adverse Event Severity and Relationship to DEX PS DDS

The investigators will rate the severity of each AE as mild, moderate, or severe.

The investigator will use the following definitions to rate the severity of each AE:

Mild	The AE is transient and easily tolerated by the subject.
Moderate	The AE causes the subject discomfort and interrupts the subject's usual activities.
Severe	The AE causes considerable interference with the subject's usual activities and may be incapacitating or life threatening.

The investigator will use the following definitions to assess the relationship of the AE to the use of DEX PS DDS:

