Appendix B. Definition of Adverse Events of Special Interest

Adverse Events of Special Interest (AESI) will be identified using the following search criteria:

Area of Safety Interest	Search Criteria
AEs related to Implant position and administration	Conjunctival hemorrhage, conjunctival tear cataract, lens or lenticular abnormality or change from baseline, vitreous haze, vitreous hemorrhage, vitreous leak, retinal hemorrhage, retinal tear, retinal hole, retinal detachment, other retinal abnormality or change, intraocular inflammation, blindness, visual acuity or vision decrease, abnormality or change of BCVA (≥ 2 lines or more worst than baseline), IOP change by 10 mmHg from baseline. Adjudicated terms will be further identified using CECAT and CETERM from the CE SDTM dataset.

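### The table of AEs tied to implant position and administration is not limited to the study eye, so fellow-eye events could be counted in it (SAP 10.2.6 and Appendix B)

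*SAP*

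**What the plan says.** SAP 10.2.6 first notes that the protocol names no AEs of special interest, then plans a table all the same: "However, AEs possibly related to DEX PS DDS implant position and administration will be tabulated by PT". A list of terms follows, among them conjunctival, vitreous and retinal hemorrhage, retinal detachment and reduced vision. Two measured criteria are added, a BCVA loss of two or more lines and an IOP change. The sentence that adds them ends "IOP change by 10 mmHg from baseline will be reported as AE, and will be included".

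SAP Appendix B repeats the list under the lead-in "Adverse Events of Special Interest (AESI) will be identified using the following search criteria" and closes with "Adjudicated terms will be further identified using CECAT and CETERM from the CE SDTM dataset". In the AE overview (SAP 10.2.2) the matching row reads "Any AEs of Special Interest". None of these three places names an eye.

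Other parts of the SAP do:
- Sections 10.2.1 and 10.2.3 refer to "ocular treatment-emergent AEs in either the study eye or fellow eye".
- Section 10.5.1 tabulates BCVA for the study eye and the fellow eye.
- Section 10.5.2 limits both the IOP cut-offs and the 10 mmHg increase to the study eye.
- Section 10.1 defines the study eye as the one that received the implant.

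On the fellow eye, Protocol 5.4 (Table 1) states: "Treatment in the non-SE is not restricted during the study, and the non-SE will receive standard of care per investigator discretion". Eligibility criterion 16 bars other intravitreal injections in the study eye only.

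**The concern.** The table is labelled as showing events of implant position and administration, yet its selection rule is a term search with no condition on the eye. A conjunctival hemorrhage after a routine fellow-eye injection matches a listed term. So does a retinal hemorrhage from retinal disease in the fellow eye. For BCVA and IOP the rule contains no judgment step at all: the change is recorded as an AE and included.

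Such events say nothing about either applicator. The study has no hypothesis test, so readers will look directly at the counts and percentages. In arms this small, a few events from the wrong eye would visibly raise the rate reported under this label.

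**Working it through.** **1. Planned arm sizes.** Protocol 7.8 and SAP 2.4 give minimums of 30 and 15 eyes, dropout of about 15% and a total of about 54; allocation is 2:1.
- Updated: 30 / (1 − 0.15) = 35.3, rounded up to 36.
- Currently approved: 15 / (1 − 0.15) = 17.6, rounded up to 18.
- Total: 36 + 18 = 54, which reproduces the plan's figure. No stated number is in dispute.

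**2. Weight of one misplaced subject.**
- Updated arm: 1/36 = 2.8 points (1/30 = 3.3 points at the minimum).
- Comparator arm: 1/18 = 5.6 points (1/15 = 6.7 points at the minimum).

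**3. Can a fellow-eye event reach the table?**
- *Detection:* the Activity Schedule (Protocol Appendix D) has BCVA, IOP, slit lamp and ophthalmoscopy in both eyes at baseline, Day 2 and Day 7.
- *Source:* fellow-eye treatment is unrestricted, and the injection ban covers the study eye only.
- *Selection:* the terms in 10.2.6 and Appendix B carry no eye condition.
- *Contrast:* 10.5.2 applies the 10 mmHg increase to the study eye, while 10.2.6 uses a 10 mmHg change with no eye stated.

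Each step is open, so the rule as written admits the event.

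**4. Does the missing treatment-emergent wording matter?** Seven of the nine overview rows in 10.2.2 say treatment-emergent; the special-interest row and the all-deaths row do not. The practical gap is very small:
- Before dosing, only procedure-related AEs are collected (Protocol 6.1: "study procedure-related serious and nonserious AEs will be collected from the time the subject signs the study-specific informed consent").
- Screening lasts a few days at most and involves no injection.
- BCVA and IOP are not scheduled again until Day 2, so the measured criteria cannot arise from a scheduled pre-injection visit.
- SAP 10.2.1 treats onset on the dosing day as treatment-emergent, so adding the wording would not remove same-day events before injection.

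**5. Illustration of frequency (assumed inputs only).** The documents give no rate of fellow-eye injection and no event rate per injection. Suppose a share f of 10% to 30% of subjects have such an injection while AEs are collected, and a share q of 10% to 30% of those have a listed AE. The share affected is p = f × q.
- Low end: 0.10 × 0.10 = 1%. Expected 36 × 0.01 = 0.4 and 18 × 0.01 = 0.2 subjects. Chance of at least one among 54: 1 − 0.99^54 = 42%.
- High end: 0.30 × 0.30 = 9%. Expected 36 × 0.09 = 3.2 and 18 × 0.09 = 1.6 subjects. Chance of at least one: 1 − 0.91^54 = 99%.

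The width of that range shows that the frequency is unknown. With a study-eye limit the contribution is zero under any inputs.

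**The case against.** The best defense is that the SAP does not select by terms alone. Section 10.2.6 speaks of AEs possibly related to position and administration, and on a plain reading a hemorrhage from a fellow-eye injection is not related to an implant in the other eye. Appendix B also mentions adjudicated terms. This stands in part: a reader might infer that fellow-eye events will be held against the applicators, and the text supports only that they could be. It does not close the gap. No assessor, rule or eye is given for the relatedness judgment or the adjudication, and the BCVA and IOP criteria are included without either.

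A second defense is that the information exists elsewhere. SAP 10.2.3 tabulates ocular treatment-emergent AEs by relationship to the study procedure, BCVA and examination findings are tabulated for each eye, and 10.5.2 gives the IOP increase in the study eye. This stands. It would be wrong to call 10.2.6 the only AE table that bears on the applicator. The label on this table would still not match its content.

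Third, assignment is randomized, the trial makes no formal comparison, and applicator performance is judged on the Day 1 assessment form. This also stands, and it limits the consequence to absolute rates and noise.

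**Conclusion.** The concern holds in a limited form. The definition in SAP 10.2.6, Appendix B and the 10.2.2 overview row has no study-eye condition, so fellow-eye events could be counted as events of implant position and administration. Each such subject adds 2.8 points in an arm of 36 or 5.6 points in an arm of 18. How many there would be cannot be derived from the documents; the range in the working rests on assumed rates.

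Three stronger conclusions might be inferred and are not supported:
- *Bias toward one applicator.* Randomization balances fellow-eye events on average; what remains is inflated rates and chance imbalance.
- *Contamination by pre-injection events.* The collection rule, the visit schedule and the same-day convention leave almost nothing there, so the onset wording is a minor point of consistency.
- *Damage to the main conclusion.* The primary objective concerns delivery to the vitreous cavity, and the assessment form addresses that directly.

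It should still be corrected, because the label promises something the selection rule does not deliver and the correction is easy.

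**What to change.** In SAP 10.2.6, Appendix B and the 10.2.2 overview row:
- define the set as treatment-emergent AEs whose eCRF location includes the study eye;
- apply the BCVA and IOP criteria to the study eye, as 10.5.2 already does for the 10 mmHg increase;
- show the same terms for the fellow eye in a separate column or listing;
- state how the adjudicated-terms step in Appendix B applies the study-eye limit.

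The cost is a sentence in each of three places, one sentence on adjudication, and a programming filter on AE location and onset date, which the SAP already uses in 10.2.1. No new data or procedures are required. Settling it before tables are produced avoids deciding which eye's events to keep once results are visible in an open-label study.
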